7.1 Sample Size Determination

Twenty subjects will be evaluated to determine the safety profile of chelation in this setting and to provide information on potential endpoints for future studies in this area. The distributions of urinary measures of Gd excretion as well as for pain and quality of life will be evaluated at baseline and after each treatment, as will the differences in these measures between baseline and each treatment.

7.2 Statistical Methods

Changes between baseline and each treatment will be evaluated for direction and magnitude. Although the goal is estimation of effect size and variation, statistical tests for changes pre/post treatment will be evaluated to understand the pre/post changes toward development of a future trial. These tests will evaluate the null hypothesis of no change in urine measures or symptoms (via questionnaire). If the changes in measures are normally distributed, then paired t-tests will be used. However, it is more likely that the data will not be normally distributed and that Wilcoxon signed-rank tests will be need. For any nominal (yes/no) questionnaire data, a McNemar's or sign test will be used for the paired contingency table. Since these tests will likely be used in future studies, direction of effect measures (differences) and ranges of estimates (confidence intervals) will provide information on what to expect in testing and analyzing more individuals

Subject Population(s) for Analysis

All-treated population: All subjects consenting to study will be treated with the same therapy, receiving at least one dose of study drug.

8 Safety and Adverse Events

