10	STUDY MONITORING, AUDITING, AND INSPECTING	17
10.1	STUDY MONITORING PLAN.....	17
10.2	AUDITING AND INSPECTING	17
11	ETHICAL CONSIDERATIONS	17
12	STUDY FINANCES	17
12.1	FUNDING SOURCE.....	17
12.2	CONFLICT OF INTEREST	17
13	PUBLICATION PLAN	18
14	REFERENCES	18
15	APPENDICES (.....	18

List of Abbreviations

DTPA—Diethylene Triamine Penta-acetic Acid

Gd—Gadolinium

GBCA—Gadolinium Based Contrast Agent

MRI—Magnetic Resonance Imaging

Study Summary

Title	INVESTIGATOR-INITIATED INVESTIGATIONAL NEW DRUG (IND) APPLICATION TO STUDY THE EFFECTS OF INTRAVENOUSLY ADMINISTERED CA-DTPA AND ZN-DTPA TO TREAT PATIENTS WITH GADOLINIUM DEPOSITION DISEASE
Short Title	Ca/Zn DTPA for GDD
Protocol Number	GDD-001
Phase	Feasibility study
Methodology	Open label, non-randomization
Study Duration	1 year
Study Center(s)	Single center
Objectives	To see an increase in the elimination of Gd as measured by analysis of 24 hour urine collections.
Number of Subjects	20
Diagnosis and Main Inclusion Criteria	Gadolinium Deposition Disease (GDD)— *Symptoms of pain, depressed levels of consciousness, and skin induration post administration of a GBCA as well as elevated levels of gadolinium in 24 hr urine, greater than 30 days post administration of a GBCA
Study Product, Dose, Route, Regimen	Ca –DTPA (0.5 gm) administered IV push over 1 minute at the beginning of infusion, along with normal saline (over a 90 minute period), ending with another 0.5 gm DTPA dose with 10 minutes left of saline infusion. This will be followed the next day with Zn-DTPA (0.5 gm) administered IV push over 1 minute with normal saline (over a 90 minute period), ending with another 0.5 gm DTPA dose with 10 minutes left of saline infusion. A total of 1 gm of DTPA is administered at each treatment. This sequence will be administered 3 times, approximately 1 month apart.
Duration of administration	3 months
Reference therapy	No treatments established for this condition
Statistical Methodology	R, a language and environment for statistical computing (R Core Team, Vienna, Austria), will be used for all statistical computing. Statistical significance will be defined as p value less than 0.05.

1 Introduction

[figure not shown]

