3.3 Secondary Study Endpoints

To observe increased elimination of gadolinium in 24-hour urine collections post infusion therapy, estimated at greater than two-fold increase.

The pre-chelation Gd amount in urine should decrease from the first to third treatment.

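### The urine gadolinium endpoint is a more than two-fold increase, but Section 7.2 tests only no change and reports differences, by a method left to an unspecified normality check

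*Combined protocol and SAP*

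**What the plan says.** Section 3.3 describes the urine Gd endpoint as increased elimination after infusion, "estimated at greater than two-fold increase". Increased elimination is also the primary objective in Section 2.

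The analysis is in Section 7.2. Its hypothesis is: "These tests will evaluate the null hypothesis of no change in urine measures or symptoms (via questionnaire"). Its selection rule is: "If the changes in measures are normally distributed, then paired t-tests will be used". It then says that "it is more likely that the data will not be normally distributed and that Wilcoxon signed-rank tests will be need". On reporting, "direction of effect measures (differences) and ranges of estimates (confidence intervals) will provide information on what to expect". Section 7.2 also says that "the goal is estimation of effect size and variation".

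The Study Summary adds: "Statistical significance will be defined as p value less than 0.05". Section 7.1 sets the size without a power calculation: "Twenty subjects will be evaluated to determine the safety profile of chelation in this setting".

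Section 7 names no ratio, log scale, normality test, cut-off or interval method. It does not say whether the intervals are for a mean, a median or a pseudomedian.

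**The concern.** The endpoint and the analysis are on different scales. A fold increase is relative to each subject's own baseline, while a difference is in absolute units. Neither planned test refers to the value 2, and an interval for a difference cannot be turned into an interval for a fold change.

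The selection rule adds a second problem. With skewed changes, the mean (t-test branch) and the pseudomedian (the Hodges-Lehmann estimate that goes with the signed-rank test) are different quantities. The sample would decide which one is reported, and different collections in the same study could end up on different branches.

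What is at stake is the study's main statistical product. Section 7.2 puts estimation ahead of testing and says the results are meant to inform a later trial. A planner who needs the typical fold increase and its precision would not get either from the analysis as written.

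**Working it through.** **Inputs from the documents.** n = 20, paired, single arm (Section 7.1); significance level 0.05 (Study Summary); null of no change (Section 7.2); endpoint ratio above 2 (Section 3.3). Sidedness is not stated, so two-sided 95% intervals are assumed. There is no stated power or precision figure to reproduce.

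**Assumed inputs.** No SD or shape for urine Gd is given. The ranges used are a log-ratio SD *s* of 0.3 to 0.8, a baseline log-SD of 0.5 to 1.2, and log-normal data unless stated.

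**1. A difference does not fix a ratio.** A change from 1 to 3 and a change from 10 to 12 are both +2. The first is 3/1 = 3-fold and the second is 12/10 = 1.2-fold. No distributional assumption is needed here.

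**2. Rejecting no change does not show two-fold.** Suppose the true ratio is 1.5, below the endpoint. For a t-test on log-ratios the noncentrality is ln(1.5)/(s/√20), with 19 degrees of freedom and critical value 2.093.

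| s | noncentrality | P(reject no change) |
|---|---|---|
| 0.3 | 0.4055/0.0671 = 6.04 | >0.99 |
| 0.5 | 0.4055/0.1118 = 3.63 | 0.93 |
| 0.8 | 0.4055/0.1789 = 2.27 | 0.58 |

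This log-scale calculation illustrates the point. The planned tests on differences have no two-fold reference either.

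**3. What a log-ratio interval would give.** The 95% limits are the geometric mean ratio divided and multiplied by exp(2.093 × s/√20). The lower limit exceeds 2 when the observed ratio exceeds 2 times that factor. If the true ratio is exactly 2, this happens with probability 0.025. If the true ratio is 3, the distance from 2 is ln(3/2) = ln(1.5), so the probabilities equal those in step 2.

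| s | factor | observed ratio needed | P(lower limit > 2), true ratio 3 | true ratio 4 |
|---|---|---|---|---|
| 0.3 | 1.151 | 2.30 | >0.99 | >0.99 |
| 0.5 | 1.264 | 2.53 | 0.93 | >0.99 |
| 0.8 | 1.454 | 2.91 | 0.58 | 0.96 |

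**4. Interval coverage by target.** These are simulations at n = 20 with 6,000 replicates (standard error √(0.95 × 0.05/6000) ≈ 0.003). Shapiro-Wilk at 0.05 stands in for the unnamed normality check.
- t interval for the mean difference (baseline log-SD 0.8, s of 0.5 or 0.8, median fold change 1 to 2): about 82% to 92%.
- Wilcoxon/Hodges-Lehmann interval for its own pseudomedian: about 94% to 95%.
- Two-stage procedure, judged against the target of whichever branch was chosen (fold change 2 to 10, wider SD range): 91% to 94%. Normality was accepted in 0.7% to 35% of these skewed samples.
- Log-ratio t interval for the geometric mean ratio: 94.3% to 95.7% with log-normal data and fold change 2 or more. It falls to about 91% to 92% if the log-ratios are strongly skewed (exponential shape).

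**5. False positives.** With baseline log-SD 0.8 and pre and post values exchangeable, so that there is truly no change, the two-stage procedure rejected 4.5% (s = 0.5) and 4.8% (s = 0.8) of the time. The log-ratio t-test rejected 4.6% and 5.2%.

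**The case against.** The strongest defence is that this is an open-label feasibility study of 20 subjects, that its tests are secondary to estimation, and that no decision hangs on them. The two-fold wording can be read as an expectation rather than a threshold to be tested. Section 7.2 also promises to look at the magnitude of change, so fold changes could be reported from the same data. Nothing there expressly forbids a log scale, and the log-ratio is not the only suitable choice: a signed-rank analysis of the log-ratios, or of post minus twice baseline, would also address two-fold.

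Much of this stands, and it limits how serious the point is. It does not close the gap. The only effect measure that Section 7.2 names is a difference, and a fold change that could be reported is not one that has been pre-specified with an interval.

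A reader might also infer two stronger things. The first is that the planned intervals under-cover in general. The documents do not support that: they name no interval target, and the branch the plan expects to need covers its own target at about 94% to 95%. Material under-coverage is confined to the t interval for the mean difference, under assumed skewness.

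The second is that choosing the test from the data inflates the false-positive rate. Step 5 shows about 5% under a true null of no change. Rates above 5% appear if only the median fold change is set to 1, but the mean ratio is then exp(s²/2), which is 1.13 at s = 0.5 and 1.38 at s = 0.8. The mean difference is not zero in that setting, so those rejections are not false positives.

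**Conclusion.** The point holds as a mismatch between endpoint and analysis. Followed as written, Section 7.2 yields no estimate or interval that answers the more than two-fold endpoint in Section 3.3, and an undefined normality check decides which quantity is estimated. This rests on the text alone.

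The numerical size rests on assumed SDs. With a true ratio of 1.5, a log-scale test of no change would be significant with probability 0.58 to above 0.99, although the endpoint was not met. The coverage results are secondary and also conditional on assumption. The log-ratio interval should not be presented as a repair of the same interval: it changes the target to the geometric mean ratio, and it is not immune to skewness. The change is worth making before analysis, but it does not threaten the conduct of the study.

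**What to change.** In Section 7.2, for urine Gd:

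- Make log(post/baseline) at each treatment the single pre-specified analysis. Report the geometric mean fold change with a t-based 95% confidence interval, compared with 1 and with 2.
- Give the signed-rank analysis of the log-ratios, with its Hodges-Lehmann interval, as a fixed sensitivity analysis.
- Drop the normality-based choice of method for this measure.
- State which collections serve as baseline and post. The Time and Events Table has one collection before treatment and two in each treatment round.
- State how values below the assay limit are handled, with a sensitivity check.

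While editing, reconcile the status of Gd elimination, which is the primary objective in Section 2 but a secondary endpoint in Section 3.3.

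The cost is a few sentences and no extra data. The small downside is the assay-limit rule, because log-ratios can be sensitive to it. Entry requires an elevated 24-hour urine result, which makes log-ratios workable, but that result may predate the Visit 0 collection, so low baseline values cannot be ruled out.

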8.1 Definitions

Unanticipated Problems Involving Risk to Subjects or Others

Any incident, experience, or outcome that meets all of the following criteria:

- Unexpected in nature, severity, or frequency (i.e. not described in study-related documents such as the IRB-approved protocol or consent form, the investigators brochure, etc)
- Related or possibly related to participation in the research (i.e. possibly related means there is a reasonable possibility that the incident experience, or outcome may have been caused by the procedures involved in the research,

- Serious (as defined below) “**Serious**” is different than “severe” as reported in the CTC criteria that applies a grade to the AE.

Adverse Event

An **adverse event** (AE) is any symptom, sign, illness or experience that develops or worsens in severity during the course of the study. Intercurrent illnesses or injuries should be regarded as adverse events. Abnormal results of diagnostic procedures are considered to be adverse events if the abnormality:

- results in study withdrawal
- is associated with a serious adverse event
- is associated with clinical signs or symptoms
- leads to additional treatment or to further diagnostic tests
- is considered by the investigator to be of clinical significance

Serious Adverse Event

Adverse events are classified as serious or non-serious. A **serious adverse event** is any AE that is:

- fatal
- life-threatening
- requires or prolongs hospital stay
- results in persistent or significant disability or incapacity
- a congenital anomaly or birth defect
- an important medical event

Important medical events are those that may not be immediately life threatening, but are clearly of major clinical significance. They may jeopardize the subject, and may require intervention to prevent one of the other serious outcomes noted above. For example, drug overdose or abuse, a seizure that did not result in in-patient hospitalization or intensive treatment of bronchospasm in an emergency department would typically be considered serious.

All adverse events that do not meet any of the criteria for serious should be regarded as **non-serious adverse events**.

For the purpose of this trial, the following will be considered expected adverse events:

Ca-DTPA—headache, lightheadedness, chest pain, allergic reaction, dermatitis, metallic taste, nausea and diarrhea, and injection site reactions.

Zn-DTPA—headache, lightheadedness, and pelvic pain.

Possible “flare effect”, resulting in exacerbation of current symptoms.

Adverse Event Reporting Period

The study period during which adverse events must be reported is normally defined as the period from the initiation of any study procedures to the end of the study treatment follow-up. For this study, the study treatment follow-up is defined as 30 days following the last administration of study treatment.

Preexisting Condition

A preexisting condition is one that is present at the start of the study. A preexisting condition should be recorded as an adverse event if the frequency, intensity, or the character of the condition worsens during the study period.

General Physical Examination Findings

At screening, any clinically significant abnormality should be recorded as a preexisting condition. At the end of the study, any new clinically significant findings/abnormalities that meet the definition of an adverse event must also be recorded and documented as an adverse event.

Post-study Adverse Event

All unresolved adverse events should be followed by the investigator until the events are resolved, the subject is lost to follow-up, or the adverse event is otherwise explained. At the last scheduled visit, the investigator should instruct each subject to report any subsequent event(s) that the subject, or the subject's personal physician, believes might reasonably be related to participation in this study. The investigator should notify the study sponsor of any death or adverse event occurring at any time after a subject has discontinued or terminated study participation that may reasonably be related to this study. The sponsor should also be notified if the investigator should become aware of the development of cancer or of a congenital anomaly in a subsequently conceived offspring of a subject that has participated in this study.

Abnormal Laboratory Values

A clinical laboratory abnormality should be documented as an adverse event if any one of the following conditions is met:

- The laboratory abnormality is not otherwise refuted by a repeat test to confirm the abnormality
- The abnormality suggests a disease and/or organ toxicity
- The abnormality is of a degree that requires active management; e.g. change of dose, discontinuation of the drug, more frequent follow-up assessments, further diagnostic investigation, etc.

Hospitalization, Prolonged Hospitalization or Surgery

Any adverse event that results in hospitalization or prolonged hospitalization should be documented and reported as a serious adverse event unless specifically instructed otherwise in this protocol. Any condition responsible for surgery should be documented as an adverse event if the condition meets the criteria for an adverse event.

Neither the condition, hospitalization, prolonged hospitalization, nor surgery are reported as an adverse event in the following circumstances:

- Hospitalization or prolonged hospitalization for diagnostic or elective surgical procedures for a preexisting condition. Surgery should **not** be reported as an outcome of an adverse event if the purpose of the surgery was elective or diagnostic and the outcome was uneventful.
- Hospitalization or prolonged hospitalization required to allow efficacy measurement for the study.
- Hospitalization or prolonged hospitalization for therapy of the target disease of the study, unless it is a worsening or increase in frequency of hospital admissions as judged by the clinical investigator.

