3.1 General Design

This is an open-label study. Patients will be evaluated at a baseline visit to determine eligibility and obtain informed consent before proceeding on to study-related procedures. Most patients coming for treatment will have had prior gadolinium testing greater than 30 days post MRI/contrast agent that shows an elevated result, thus eligibility for chelation therapy.

In addition to previous gadolinium testing, subjects will be instructed to perform a 24-hour urine collection (at visit 0) to determine a baseline for evaluating the elimination of gadolinium before initiating the first treatment.

At the first and subsequent chelation therapy visits, a baseline blood pressure will be obtained, an IV will be placed by Vascular Interventional Radiology (VIR) nursing staff, and 1L of normal saline will be connected. Initially, 2.5 mL of Ca-DTPA (1 g/5 mL) will be administered over a period of 1 minute. Five (5)

minutes post DTPA blood pressure will be collected again. The saline will then be administered at a rate of 300 mL/hr over 30 minutes with the patient seated and with hands lowered by their sides to allow the chelator to dwell slightly in the soft tissues of the hands and feet. The patient will then be positioned in a supine position on a hospital bed/gurney and the infusion rate will then be increased to 750 mL/hr over the next 60 minutes. With 10 minutes remaining (80 minutes after the start of infusion), the remaining 2.5 mL of Ca-DTPA will be administered I.V. over a period of 1 minute. The infusion of saline will continue another 9 minutes, and the I.V. line will then be removed. The patient will be instructed to drink plenty of fluids that evening. The following day, the treatment will be repeated using Zn-DTPA.

The patient will be instructed to collect 24-hour total urine samples beginning once chelation therapy starts, and bring back to the lab the following days.

The process will be repeated monthly, for a total of 3 chelation treatment time-points.

Patients will come to clinic for follow up to be assessed for adverse events one week following each treatment. Patients will be asked to fill out pain/QOL questionnaires and given a brief physical exam. Patients who live greater than 3 hours away will be assessed via phone call and instructed to get labs drawn locally. Patients may be advised to seek medical attention if the investigator feels any adverse reaction is not expected or is severe.

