6.8 **Visit 7-** The patient will return to the hospital to drop off 24-hour urine for gadolinium testing, as well as a creatinine clearance. Blood chemistries calcium, zinc, magnesium and manganese will be evaluated, along with BUN, creatinine, sodium, potassium, chloride, phosphorus and CO₂.

6.9 **Visit 8-** One week post treatment follow up visit for health assessments as before. Third therapy session will be scheduled for one month out.

6.10 **Visit 9-** Patient returns for final round of infusion therapy to be done exactly as first two treatments with day one of Ca-DTPA, including pregnancy testing on women of child-bearing potential and pain assessment sheets for the week. Blood samples will be collected by phlebotomy trained staff at the Clinical & Translational Research Center (CTRC) at UNC Memorial hospital. Patient blood samples will be obtained just prior to intravenous administration of Ca-DTPA or Zn-DTPA

6.11 **Visit 10-** Patient returns for day two of infusion therapy with Zn-DTPA. Blood samples will be collected by phlebotomy trained staff at the Clinical & Translational Research Center (CTRC) at UNC Memorial hospital. Patient blood samples will be obtained just prior to intravenous administration of Ca-DTPA or Zn-DTPA

6.12 **Visit 11-** The patient will return to the hospital to drop off 24-hour urine for gadolinium testing, as well as a creatinine clearance. Blood chemistries calcium, zinc, magnesium and manganese will be evaluated, along with BUN, creatinine, sodium, potassium, chloride, phosphorus and CO₂.

6.13 **Visit 12-** Subject returns for final follow up assessments 1 week (+5 days) following last infusion therapy. If patient lives more than 3 hours away, a phone-call will be done by the treating physician or clinician.

6.14 **Visits 13-14-** Subjects will receive a phone call from the coordinator to go over pain the pain assessment scale at months 6 and 12 following treatment.

At any time in between treatments if the clinician or patient feels they need to be seen, they will be brought in to the clinic (or to their local healthcare provider) for evaluation and possible discontinuation of therapy.

7 Statistical Plan

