8.2 Recording of Adverse Events

At each contact with the subject, the investigator must seek information on adverse events by specific questioning and, as appropriate, by examination. Information on all adverse events should be recorded immediately in the source document, and also in the appropriate adverse event module of the case report form (CRF). All clearly related signs, symptoms, and abnormal diagnostic procedures results should be recorded in the source document, though should be grouped under one diagnosis.

All adverse events occurring during the study period must be recorded. The clinical course of each event should be followed until resolution, stabilization, or until it has been determined that the study treatment or participation is not the cause. Serious adverse events that are still ongoing at the end of the study period must be followed up to determine the final outcome. Any serious adverse event that occurs after the study period and is considered to be possibly related to the study treatment or study participation should be recorded and reported immediately.

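### Adverse events are reportable for 30 days after the last dose, but after round 3 no contact is scheduled between Visit 12 (1 week, +5 days) and the month 6 call

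*Combined protocol and SAP*

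**What the plan says.** **Reporting period.** Section 8.1 (Adverse Event Reporting Period) makes AEs reportable over "the period from the initiation of any study procedures to the end of the study treatment follow-up", and adds that "the study treatment follow-up is defined as 30 days following the last administration of study treatment". Section 8.2 requires every AE in the study period to be recorded.

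**How AEs are found.** Section 8.2: "At each contact with the subject, the investigator must seek information on adverse events by specific questioning". Section 3.1 gives the one-week visits an explicit AE purpose: "Patients will come to clinic for follow up to be assessed for adverse events one week following each treatment".

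**Contacts after the last dose (Section 6).**
- Visit 10 is the last dose: "Patient returns for day two of infusion therapy with Zn-DTPA".
- Visit 11, the next day, is for urine drop-off and blood chemistries.
- Visit 12: "Subject returns for final follow up assessments 1 week (+5 days) following last infusion therapy". It may be done by telephone for patients living far away.
- Visits 13 and 14 are coordinator calls to go over the "pain assessment scale at months 6 and 12 following treatment". The Time and Events Table adds quality of life.

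Neither Section 6 nor the table shows a visit or call at or near day 30 after the last infusion.

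**Other routes.** Section 8.1 has subjects told, at the final scheduled visit, to report later events that they or their physician think may be related to the study. It also has unresolved AEs followed. Section 8.2 requires possibly related serious AEs arising after the study period to be recorded and reported.

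**The concern.** The plan sets a 30-day duty to report all AEs and relies on questioning at contacts to find them, but it schedules no contact that can close the window after the final round. Section 7.1 gives evaluation of the safety profile as a reason for enrolling the 20 subjects, so completeness of AE data bears directly on what the study is for. AEs arising after Visit 12 would be collected less reliably than those before it, and the final summary would not show that. The gap is confined to the third round. After rounds 1 and 2 the patient returns for the next infusion about a month later (Visits 5 and 9), and the Section 8.2 rule makes those visits AE contacts.

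**Working it through.** There is no derived figure in the plan to reproduce. The check is schedule arithmetic.

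**Inputs**
- Reporting window: 30 days from the last administration (Section 8.1).
- Last administration: Visit 10, day 2 of the third round (Section 6.11).
- Last scheduled contact inside the window: Visit 12, day 7 to day 12 after the last infusion (Section 6.13).
- Next scheduled contact: the month 6 call (Section 6.14).

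**Days with no scheduled contact** = 30 − day of Visit 12; share = that number / 30.

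| Timing of Visit 12 after last dose | Days left | Share of window |
|---|---|---|
| Day 12 (1 week + 5 days) | 30 − 12 = 18 | 18/30 = 60% |
| Day 7 (1 week) | 30 − 7 = 23 | 23/30 = 77% |

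*Sensitivity to the day count.* The table labels Visit 12 as Day 7, with Zn-DTPA on Day 2. If Day 7 is counted from the first infusion of the round, Visit 12 falls 7 − 2 = 5 days after the last dose. That leaves 30 − 5 = 25 days (25/30 = 83%), or 30 − 10 = 20 days (67%) with the 5-day allowance. The text of Section 6.13 counts from the last infusion, so 60% to 77% is the main range. It is more than half on every reading.

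**Delay to the next contact.** Assume 30.4 days per month.
- Counted from the end of treatment, as Section 6.14 reads: 6 × 30.4 ≈ 182 days, which is 182 − 30 = 152 days after the window closes.
- Counted from study start, as the table's month labels could be read, with the last dose about 2 months in: 4 × 30.4 ≈ 122 days, which is 122 − 30 = 92 days after the window closes.

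Either way the next enquiry comes at least about three months after the window has closed.

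**Whether another provision fills the gap**
- The instruction to self-report covers only events thought related, whereas the 30-day duty covers all AEs. It is given at the final scheduled visit, which could mean Visit 12 or the month 12 call. On the second reading it comes long after day 30.
- Following unresolved AEs does not detect new ones.
- The provision for serious AEs after the study period concerns a later time and a narrower class of event.
- The unscheduled-visit provision at the end of Section 6 is worded for the time between treatments, so it does not clearly reach beyond round 3.
- The daily pain sheets stop at day 6 after treatment (Section 6.2).

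**The case against.** A reader might infer that most of the final window is unobserved and that no elicited AE data would exist for it. The documents do not support that. Section 8.2 requires AE questioning at every contact, and the month 6 call is a contact. The descriptions of Visits 5 and 9 mention no AE questions either; they count as AE contacts only through Section 8.2. The same rule must then be allowed to reach month 6. What separates round 3 from rounds 1 and 2 is the delay before the next enquiry, about one month against several. Spontaneous reports also remain possible throughout.

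A reader might also infer a biased comparison of AE rates between rounds, or a particular hazard because cumulative exposure is highest after round 3. No by-round AE analysis is planned: Section 7.2 tests urine and questionnaire measures, and Section 8.5 has AEs summarized for the final manuscript. Nor do the documents say that risk rises with total dose; Section 1.4 reports a worker given 583 g over four years without observed toxicity.

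Finally, Section 8.1 says when AEs must be reported and does not promise active questioning on every day of the window, so this is a mismatch between duty and schedule rather than a flat contradiction. The one named safety endpoint, hypocalcemia (Section 3.4), is covered by the chemistries at Visit 11.

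All of this limits the claim. None of it supplies a timely AE enquiry for the last 18 to 23 days.

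**Conclusion.** The point stands as a modest gap in AE ascertainment. After round 3, 60% to 77% of the 30-day reporting period has no scheduled contact in it or close to its end, for all 20 planned subjects if all complete treatment. AEs arising then depend on spontaneous reporting or on recall at the month 6 call. The likely direction is too few late AEs in the overall safety summary. The size is unknown, because the documents give no expected rate of late AEs and no basis for judging recall.

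The conclusion rests on Visit 12 being timed from the last infusion, as Section 6.13 states, and on there being no contact beyond those in Section 6 and the table. The urine gadolinium tests, the symptom tests and the calcium check at Visits 3, 7 and 11 do not depend on it.

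**What to change.** Reconcile the schedule with the 30-day reporting period. Add one telephone contact, with the standard AE questions, at about day 30 after the last infusion. It is best placed on or just after day 30, so that a single enquiry covers the rest of the window. Enter it in Section 6 between Visits 12 and 13, and as a column in the Time and Events Table. State who makes the call, in line with Section 8.2 (the investigator asks) and Section 8.5 (AEs are assessed by a licensed investigator). The same amendment can say which visit is meant for the self-reporting instruction in Section 8.1.

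The cost is about 20 calls, one table column, and a protocol amendment with IRB review. No new staff or procedure is needed. Collecting the pain/QOL form at the same contact is optional and not part of this fix.
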